#### **8.1.1 Participant Disposition and Study Drug Exposure**

Study disposition, demographic and baseline characteristics, and study medication exposure will be summarized for study patients. Study drug administration will be summarized, number of days of dosing, and reasons for final discontinuation of study drug.

Demographic and baseline characteristics will include race, age, sex, and selected clinical variables recorded prior to initiation of study drug.

#### **8.1.2 Safety**

The safety reports will be summarized.

Serious adverse events will be presented overall. Severity and relationship to study drug will be provided.

Events of special interest will be presented overall and summarized by participant characteristics.

Prior and concomitant medications will be summarized by World Health Organization (WHO) drug class.

## **9. ETHICAL AND REGULATORY CONSIDERATIONS**

### **9.1 Good Clinical Practice Statement**

It is the responsibility of the investigator(s) to ensure that this clinical study will be conducted in accordance with the ethical principles that have their origin in the Declaration of Helsinki, and that are consistent with the ICH guidelines for Good Clinical Practice (GCP) and applicable regulatory requirements.

The study will be conducted in accordance with US regulations (e.g. 45 CFR 46 and 21 CFR 312), the International Council for Harmonisation guidelines for Good Clinical Practice (GCP) (ICH E6),. The US Code of Federal Regulations (CFR) include but are not limited to:

- 45 CFR 46 (Human Subjects Protection)
- 45 CFR 160 and 164 Subparts A and E (Health Insurance Portability and Accountability Act [HIPAA] Privacy Rule)
- 21 CFR 312 (Investigational New Drug [IND] Application) as applicable
- 21 CFR 50 (Protection of Human Subjects, including Subpart D - Additional Safeguards for Children in Clinical Investigations)
- 21 CFR 56 (Institutional Review Boards [IRB])

### **9.2 Informed Consent**

The principles of informed consent are described in 45 CFR 46 and 21 CFR 50.

Ocular Therapeutix will have the right to review and comment on the informed consent form.

It is the responsibility of the investigator or designee (if acceptable by local regulations) to obtain written informed consent from each patient prior to his/her participation in the study and after the aims, methods, objectives, and potential hazards of the study have been explained to the patient in language that he/she can understand. The ICF will be signed and dated by the patient and by the investigator or authorized designee who reviewed the ICF with the patient.

Patients who can write but cannot read will have the ICF read to them before signing and dating the ICF.

Patients who can understand but who can neither write nor read will have the ICF read to them in presence of an impartial witness, who will sign and date the ICF to confirm that informed consent was given.

The original ICF will be retained by the investigator as part of the patient's study record, and a copy of the signed ICF will be given to the patient.

If new safety information results in significant changes in the risk/benefit assessment, the ICF will be reviewed and updated appropriately. All study patients will be informed of the new information and provide their written consent if they wish to continue in the study. The original signed revised ICF will be maintained in the patient's study record and a copy will be given to the patient.

### **9.3 Patient Confidentiality and Data Protection**

The investigator will take all appropriate measures to ensure that the anonymity of each study patient will be maintained.

The patient's and investigator's personal data will be treated in compliance with all applicable laws and regulations.

### **9.4 Institutional Review Board**

An appropriately constituted IRB, as described in 21 CFR 56 and 45 CFR 46 will review and approve:

- The protocol, ICF, and any other materials to be provided to the patients (e.g. advertising) before any patient may be enrolled in the study
- Any amendment or modification to the study protocol or ICF before implementation, unless the change is necessary to eliminate an immediate hazard to the patients, in which case the IRB will be informed as soon as possible

Ongoing studies will be reviewed by the IRB/EC on an annual basis or at intervals appropriate to the degree of risk.

In addition, the IRB will be informed of any event likely to affect the safety of patients or the continued conduct of the clinical study.

A copy of the IRB approval letter will be sent to Ocular Therapeutix prior to shipment of drug insert supplies to the investigator. The approval letter will include the study title, the documents reviewed, and the date of the review.

Records of the IRB review and approval of all study documents (including approval of ongoing studies) will be kept on file by the investigator.

**10. APPENDICES****10.1 Primary caregiver satisfaction survey**

Administer this questionnaire to the primary caregiver in charge of the child's post-operative eye drop administration at **day 45 (+/- 3 days) follow-up (Visit 6)**:

#	Questions	Strongly Disagree 1	Disagree 2	Not Sure 3	Agree 4	Strongly Agree 5
1.	The instructions I was given on how to administer my child's eye drop treatment were clear and easy to follow					
2.	I did not have initial concerns regarding the administration instructions I was given on eye drop administration but some questions/issues arose for me after the dosing experience					
3.	It was difficult to fill and pick-up my child's eye drop prescription					
4.	My child's eye drops were expensive to purchase					
5.	My child cries or becomes upset when it is time to administer the eye drop treatment					
6.	Eye drop treatment appears to cause my child distress; my baby acts to avoid therapy					
7.	I sometimes forget to wash my hands prior to administering my child's eye drop treatment					
8.	It is difficult and/or frustrating to administer my child's eye drop treatment					
9.	A second person is needed to help me administer my child's eye drop treatment					
10.	I worry my child is not receiving enough eye drop treatment when I administer it					
11.	I worry I am incorrectly administering the eye drop treatment to my child					

12.	I worry I will injure my child or cause infection trying to administer the eye drop treatment					
#	Questions	Strongly Disagree	Disagree	Not Sure	Agree	Strongly Agree
13.	It takes me a while (several minutes or longer) to soothe my child or get them to settle down after administering eye drop treatment					
14.	I sometimes forget to administer my child's eye drop treatment					
15.	Administering eye drops to my child causes me stress					
16.	I am the only capable person that can administer my child's eye drop treatment and I do not trust other caregivers to administer it, such as daycare personnel, the nanny/babysitter, grandparents, etc.					
17.	I have to adjust my daily schedule in order to correctly follow my child's eye drop schedule					
18.	I would prefer a post-operative treatment regimen for my child that has fewer eye drops or none at all					

[figure not shown]

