### 2.2 Secondary Objectives

- Incidence and severity of adverse events from baseline through post-op day 45
- Degree of inflammation (AC cell count)
- Resolution of inflammation as defined as either 0 or 0.5 or less cell on follow up post op exams
- Resolution of pain using the FLACC Behavioral Pain Rating Scale
- Ratio of Intraocular pressure increase with insert
- % of patients with rebound inflammation from baseline through post-op care
- % of patients that were given supplementary prednisolone drops and the number of drops needed in these patients

- Mean change in BCVA from baseline over time using either ETDRS or HOTV chart testing depending on age
- Primary caregiver's ability to adhere to treatment plan as prescribed and therapeutic preferences measured with primary caregiver satisfaction survey

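### Caregiver survey item 2 joins two statements, so a disagree answer covers both the best and the worst experience and cannot be interpreted

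*Combined protocol and SAP*

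**What the plan says.** The last secondary objective in Section 2.2, repeated in the Synopsis, is the caregiver's ability to adhere to the treatment plan and "therapeutic preferences measured with primary caregiver satisfaction survey". The form is in Section 10.1. It has 18 statements on a five-point scale running from "Strongly Disagree 1" to "Strongly Agree 5", and it is given once, at Visit 6 (Tables 1 and 2; Section 5.2.1).

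Item 2 reads "I did not have initial concerns regarding the administration instructions I was given on eye drop administration but some questions/issues arose for me after the" and closes by referring to the experience of giving the drops. It has two clauses: the first denies concerns at the start, and the second reports problems met later. One answer is taken for both.

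Neither Section 10.1 nor Section 8 gives a scoring key, a total score or a rule for individual items. Section 8.1 plans descriptive statistics only: means and similar summaries for continuous variables, counts and percentages for discrete ones. It states that the sample of 30 is not designed to give power for differences between arms.

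**The concern.** An ordered answer is useful only if moving along the scale moves the respondent's experience in one direction. Item 2 asserts that something good was true at the start and that something bad was true later. Disagreement can arise because the first part is false, because the second part is false, or because both are.

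If the disagree box holds caregivers with opposite experiences, the arms could show the same item 2 percentages with quite different experiences behind them, or different percentages with similar experiences. A reader of the results table would probably take low codes as good news, and nothing in the data would show whether that was right. Because the survey is given only at Visit 6, the schedule offers no second administration at which to clarify an answer.

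**Working it through.** The plan states no figure for this item, so there is none to reproduce. The check is a truth table, followed by a bound on what the counts can show.

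**Inputs.** Item wording and response codes: Section 10.1. Arm sizes: Section 4.1, with 10 insert and 5 control patients in each of two procedure groups, so 2 × 10 = 20 insert and 2 × 5 = 10 control, 30 in all. Assumption: caregivers answer the sentence as written, agreeing only if both clauses are true.

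**Step 1. Truth table for item 2.**

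| Concerns at the start | Issues after dosing | First clause | Second clause | Literal answer |
|---|---|---|---|---|
| No | No | true | false | disagree |
| No | Yes | true | true | agree |
| Yes | No | false | false | disagree |
| Yes | Yes | false | true | disagree |

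Three of the four experiences give disagreement. They include the first row (no trouble at any time) and the last (trouble throughout).

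**Step 2. What the counts can show.** Let *a* caregivers in an arm agree and *d* disagree, with none marking the middle category.

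- Each of the *a* had no initial concerns and had later issues.
- Among the *d*, the number with later issues can be anything from 0 to *d*, and so can the number with initial concerns.
- In the arm as a whole, the number with later issues therefore lies between *a* and *a* + *d*, and the number with initial concerns between 0 and *d*.

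The extreme case shows the problem. If all 10 control caregivers disagree (*a* = 0, *d* = 10), the number with later issues lies between 0 and 10, that is, 0% to 100% of the arm. The item would then say nothing about whether problems arose.

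**Step 3. Can analysis repair it?** No. Reversing or regrouping the codes moves all three disagree rows together. Item 1 asks whether the instructions were clear, and items 8 and 10 to 12 ask about difficulty and worry. They give related information but do not say which row a given caregiver was in.

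**The case against.** The strongest reply is that the loss is partial. Agreement has one clear meaning, and neighbouring items cover much of the same ground. That stands, and it limits the point to the disagree side of one item. It may also be said that caregivers will not parse the sentence literally and will answer the second clause alone. Some may, but the form does not tell them to, and a caregiver who does so cannot be told apart from one who answers the whole sentence.

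A reader might go further and infer that the survey as a whole does not measure satisfaction, because agreement is favourable on item 1 ("The instructions I was given on how to administer my child's eye drop treatment were clear and easy to follow") but unfavourable to drops on items 3 to 18. The documents do not support that:

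- They define no total or mean score. Item-by-item counts, which Section 8.1 allows, are unaffected by direction, since each item's direction is plain from its wording.
- The stated construct is adherence and preferences; satisfaction appears only in the form's name. Item 14 (forgetting drops) and item 18 (preferring fewer or none) bear on that construct directly.
- Even an assumed plain sum keeps its order. With item 2 at code 1 for both, the most favourable caregiver scores 5 + 1 + 16 × 1 = 22 and the least favourable 1 + 1 + 16 × 5 = 82. Reversing item 1 (6 − x) gives 1 + 1 + 16 = 18 and 5 + 1 + 80 = 86, so the gap grows from 60 to 68. A worst plain total of 1 + 17 × 5 = 86 would need code 5 on item 2 from a caregiver whom the literal reading puts at the low end.

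Item 16 also has two clauses ("I am the only capable person that can administer my child's eye drop treatment and I do not trust other caregivers to administer it"), and a reader might class it with item 2. Its clauses point the same way, towards reliance on one caregiver, so best and worst experiences do not share a code. Splitting it is a matter of preference.

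**Conclusion.** The point holds for item 2 alone. On a literal reading, its low codes combine three of four experiences, the best and the worst among them. Disagree counts cannot be interpreted; agree counts can. This rests on the printed wording and on caregivers answering the whole sentence.

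The consequence is minor. One of 18 items is affected, under one of nine secondary objectives, in a study that is descriptive by design. The primary endpoint, the safety summaries and the survey items closest to the stated endpoint (14 and 18) do not depend on it. The absence of a scoring key is missing detail rather than an error, and would matter only if items were pooled.

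**What to change.** Replace item 2 with two items on the same scale: *I had concerns about the instructions before I started* and *Questions or problems arose after I started*. Cross-tabulated, they recover all four rows of the table above. Numbering them 2a and 2b leaves the other item numbers unchanged.

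Add to Section 8.1 that survey items are reported singly by arm, with items 14 and 18 shown on their own as the adherence and preference items, and that item 1 is reverse-coded first if items are ever pooled. A composite burden score is not advised: it would be unplanned and would bury item 14, which is direct evidence on adherence.

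The cost is one extra line on the form, a sentence or two in the analysis section, and IRB approval of the revision before use (Section 9.4). Answers to the old item 2 cannot be pooled with the new items. Any already collected should be tabulated separately, and only the agree count interpreted.

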### **4. SELECTION, WITHDRAWAL, AND REPLACEMENT OF PATIENTS**

#### **4.1 Study Population**

The study aims to enroll 30 pediatric patients undergoing routine retinal surgery or laser treatment under anesthesia. Patients in each treatment group (surgery or laser) will be randomized 2:1 at the time of surgery/laser to receive either:

- 3) Treatment Arm: Dextenza insert intraoperatively for perioperative ocular inflammation and pain. These patients will not be prescribed topical steroid drops post-operatively, or
- 4) Control Arm: Prednisolone forte 1% steroid drop taper for 28 days post-operatively to treat perioperative ocular inflammation and pain; drops four times per day (QID) on days 0-7, three times per day (TID) on days 7-14, twice per day (BID) on days 14-21 and once per day (QD) on days 21-28.

Each treatment group (surgery or laser) will include 15 patients total, 10 receiving Dextenza and 5 receiving the control drug. Drops for dilation and antibiotic coverage will be used as clinically indicated in all groups throughout the study period. Follow up will occur at post-op day 1, 7, 28/30 and 45 (+/- three days for all post-operative timepoints).

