**Table 1 Treatment Arm Schedule of Events**

Study Procedure	Screening/ Baseline	Surgical Visit Day 0	Day 1	Day 7	Day 28	Day 45
Visit	VISIT 1	VISIT 2	VISIT 3	VISIT 4	VISIT 5	VISIT 6
Windows for Visits	(Day -30 to 0)		+/- 3 days	+/- 3 days	+/- 3 days	+/- 3 days
Inclusion/Exclusion	X					
Informed Consent	X					
Demographics	X					
Medical History and Concurrent Illnesses	X					
Concomitant Medications	X					
Pregnancy testing as indicated/appropriate		X				
Subject reported AEs prior to or after surgery	X	X	X	X	X	X
Randomization with subsequent intracanalicular dexamethasone insert placement		X				
Easy of insertion		X				
If dilator was used		X				
Document administration of prescribed medications			X	X	X	X
Ocular Pain Assessment (FLACC)	X		X	X	X	X
Distance VA testing	X		X	X	X	X
BCVA (ETDRS at 4m)	X		X	X	X	X
Anterior chamber cell count	X		X	X	X	X

Study Procedure	Screening/ Baseline	Surgical Visit Day 0	Day 1	Day 7	Day 28	Day 45
Visit	VISIT 1	VISIT 2	VISIT 3	VISIT 4	VISIT 5	VISIT 6
Windows for Visits	(Day -30 to 0)		+/- 3 days	+/- 3 days	+/- 3 days	+/- 3 days
Anterior chamber cell flare	X		X	X	X	X
Punctum examination	X	X	X	X	X	X
Insert Visualization and ease of visualization score			X	X	X	X
Intraocular Pressure	X		X	X	X	X
Ophthalmic Examination (dilated fundus exam)	X		X	X	X	X
Satisfaction Survey						X

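### The caregiver survey asks only about eye drops of unspecified type, so it can describe drop burden by arm but cannot compare the insert with steroid drops on adherence, satisfaction or preference

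*Combined protocol and SAP*

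**What the plan says.** Section 2.2 and the synopsis list this secondary endpoint: "Primary caregiver's ability to adhere to treatment plan as prescribed and therapeutic preferences measured with primary caregiver satisfaction survey". Tables 1 and 2 in Section 5.1 each carry an unconditional "Satisfaction Survey" row at Day 45. Section 8.1 plans to present results by study drug against topical drops, overall and by procedure group.

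The form is in Appendix 10.1. Its instruction reads: "Administer this questionnaire to the primary caregiver in charge of the child's post-operative eye drop administration at" the Day 45 visit. It has 18 numbered statements, each rated from 1 (strongly disagree) to 5 (strongly agree), with 3 meaning not sure. A typical burden statement is item 15, "Administering eye drops to my child causes me stress". The most direct adherence statement is item 14, "I sometimes forget to administer my child's eye drop treatment". The only preference statement is item 18, "I would prefer a post-operative treatment regimen for my child that has fewer eye drops or none at all".

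On the insert arm, Section 4.1 says: "These patients will not be prescribed topical steroid drops post-operatively, or". Controls receive a 28-day prednisolone taper. Sections 4.1 and 4.3 allow dilating and antibiotic drops in both arms, with the same antibiotic regimen in each. Section 5.3 allows topical rescue drugs at the surgeon's discretion.

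**The concern.** The endpoint is about the treatment plan each child was assigned. For two thirds of the planned children that plan is an insert, and the form asks nothing about it. Control caregivers will answer mainly about prednisolone, mixed with any other drops. Insert-arm caregivers will answer about other drops or, if they gave none, about nothing. The same item then refers to different treatments in the two arms, and a by-arm table of responses could be misread as a comparison of insert with steroid drops.

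Section 1 justifies the trial partly by poor compliance with drops and by the difficulty parents have in giving them to children. The survey is the plan's main means of learning whether the insert eases that problem from the caregiver's side.

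**Working it through.** No power or effect-size calculation applies, because the plan gives none for this endpoint. The check is a count, plus a comparison of what each arm can answer.

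**1. Planned respondents (Section 4.1).** Each of the two procedure groups has 10 insert and 5 control children.
- Total: 2 × (10 + 5) = 30, which matches the stated sample size.
- Insert arm: 2 × 10 = 20. Control arm: 2 × 5 = 10.
- Insert share: 20/30, or two thirds.

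**2. Item content (Appendix 10.1).** The 18 item texts were searched.
- Items naming eye drops: 18 of 18.
- Items naming the insert (also searched as Dextenza, implant, plug or dexamethasone): 0 of 18.
- Items saying whether steroid or antibiotic drops are meant: 0 of 18.
- Items 1 to 17 presuppose that the caregiver was given drops to administer. Item 18 does not.
- No not-applicable column.

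**3. What item 14 refers to in each arm.**

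| Arm | Assigned steroid treatment | What item 14 can refer to |
|---|---|---|
| Control (10) | Prednisolone taper | Prednisolone together with any antibiotic, dilating or rescue drops, not separated |
| Insert (20) | Insert | Antibiotic, dilating or rescue drops only, or nothing |

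**4. Caregivers with something to rate on items 1 to 17.** Let p be the share of insert-arm caregivers who give any drops at home. The plan does not state p, so it is varied here as an assumption. All 10 controls are taken to give drops.

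| Assumed p | Insert-arm caregivers with drops (20 × p) | With none (20 − 20p) | Insert-arm caregivers rating the insert |
|---|---|---|---|
| 0% | 0 | 20 | 0 |
| 50% | 10 | 10 | 0 |
| 100% | 20 | 0 | 0 |

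The number with no valid answer depends entirely on p. The last column does not: even if every insert-arm child has drops at home, no item covers the assigned treatment.

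**5. Who completes the form.** The instruction addresses the person in charge of giving drops. A caregiver who gave none may fall outside it, yet Table 1 schedules the survey for every insert-arm child. Under one reading the insert arm loses respondents selectively; under the other, some respondents face 17 items they cannot validly answer.

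**The case against.** The strongest reply is that the arms can still be compared on something relevant. Insert-arm children are spared only topical steroid drops. Total drop burden, steroid plus other drops against other drops alone, can therefore be described by arm, and having fewer drops to rate is partly the intended benefit. Every caregiver can answer item 18. This stands. A reader might infer that the survey cannot compare the arms at all, and the documents do not support that.

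A reader might also infer that a total score would mix directions, because item 1 is worded favourably while most items describe burden, or that caregivers without drops would shift scores by two points by ticking 1 or 3. Neither is supported. The protocol defines no total, Section 8.1 plans descriptive summaries, and nothing in the documents indicates how such caregivers would tick.

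Adherence has other sources too. Section 5.2.1 has staff record prescribed medication and the number of drops used after surgery, and check the insert in the treatment arm. The insert is placed during the procedure, so the caregiver has no dosing task. This softens the loss on adherence, but the endpoint names the survey as its measure, and those records say nothing about satisfaction or preference.

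Finally, this is one of several secondary endpoints in a 30-patient feasibility study not powered for arm differences. That limits the severity. It does not answer the point, which concerns what the items measure rather than precision.

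**Conclusion.** The concern holds in this limited form. As written, the survey can describe general eye-drop burden by arm. It cannot compare the insert with steroid drops on adherence, satisfaction or preference, because 0 of its 18 visible items concern the treatment assigned to 20 of the 30 children. Agreement with item 18 shows a wish for fewer drops; it does not show a preference for the insert, which the item does not name.

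The content gap is certain for the numbered items. The number of insert-arm caregivers with no valid answer to items 1 to 17 is not: it runs from 0 to 20 with the unstated share who give drops at home. A figure after item 18 is missing from the text available, so further survey content there could not be checked. The point is worth correcting, but no primary conclusion depends on it.

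**What to change.** Revise the form in Appendix 10.1:
- Add a not-applicable option.
- State for each item whether it refers to steroid drops or other drops.
- Have the primary caregiver complete it in both arms whether or not drops were given, so that the instruction agrees with Tables 1 and 2.
- Add a few regimen-neutral items, worded identically in both arms: ease of following the assigned treatment, child distress, overall satisfaction, and whether the caregiver would choose the assigned treatment again.

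In Section 8.1, base the between-arm description of adherence and preference on the common items. Report the existing items only as drop burden among caregivers who gave drops, with that number shown per arm. Those caregivers are a subset defined after randomisation, so the contrast is descriptive only.

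A forced choice between insert and drops is not recommended, since most caregivers will have experienced only one regimen.

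If the form cannot be changed, relabel the endpoint as eye-drop burden. The cost is one revised form with IRB approval and a slightly longer questionnaire. Caregivers already surveyed will lack the new items, so the common-item summaries would cover only those surveyed after the change.
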